# 22. DEVELOPMENT OF A NEW PRODUCT/ PROCESS OR THE GENERATION OF INTELLECTUAL PROPERTY

Analyses and conclusions of study data and proposals of redesign of NHS services based on them ('foreground intellectual property') will be the intellectual property of West Essex CCG, as will the right to exploit analysis derived from the study data. Intellectual property related to use of the devices used from recording health measurements ('background intellectual property') vests in L2S2 Ltd. Ownership of IP generated by employees of L2S2 vests in L2S2 Ltd and exploitation is managed by L2S2 Ltd.

#### 23. ARCHIVING

[figure not shown]
Copies of all reports and analytics will be copied to the West Essex CCG at the end of the study. L2S2 will hold the anonymised data for three years and copies of all study materials for seven years after the closure of the project in the company's secure storage facilities in Cambridge UK as described in the participants' brochure.

#### 24. APPENDIX A: STUDY FLOW CHART

## **WECCGPoC Overview**

WECCGPoC Protocol Overview Version 1v1 04-12-2019

PG

#### 25. APPENDIX B: AMENDMENT HISTORY

Amendment No.	Protocol Version No.	Date issued	Author(s) of changes	Details of Changes made
1	2.0	09/03/2020	[name]	Numerous revisions to align RP to new processes
2	2.1	03/06/2020	[name]	COVID thresholds
3	2.2	11/06/2020	[name]	Aligned with latest government COVID guidelines

List details of all protocol amendments here whenever a new version of the protocol is produced. Protocol amendments must be submitted to the Sponsor for approval prior to submission to the REC committee and HRA (where required).

## 26. Appendix D NHSD comorbid conditions

The attached spreadsheet lists the Snomed codes for comorbid conditions that will be extracted from Accident and Emergency Department ECDS data. This data together with GP data and the collected data from wearables and appropriate medical devices will be used to build models to test the study hypothesis.

[name], the Chief Investigator for this study was responsible for the design and deployment of the ECDS to all Accident and Emergency Departments in England in 2018 as the national database for emergency medicine.

#### 27. Appendix E COVID-19 Procedures

Specific COVID-19 procedures have been added to the monitoring app and the care home staff research assistant's SOP.

Phase 1 of the trial was suspended because of the onset of COVID-19 in the UK. It was clear in February 2020 that visiting care homes would be unsafe and the UK was put into lockdown by the government on 23 March to attempt to limit the spread of coronavirus.

It appears that the government will gradually lift lockdown rules from June 2020 but it will be necessary to continue shielding of vulnerable participants for the foreseeable future. The study cohort is focussed on the over 65s with multiple co-morbidities and this group will be particularly susceptible to harm by COVID-19. It would not be possible to visit care homes under the government guidelines that state that care homes should restrict all non-essential healthcare visits.

The trial protocol has been revised to avoid the need for physical contact with the care homes and participants.

The Reassure app used to collect data in this trial has been updated to include secure video conferencing and safety features that make it possible to conduct the trial remotely and yet still obtain reliable data. The app is already in use in NHS hospitals to allow remote monitoring of participants at home during COVID-19.

Before COVID-19 it was intended that staff in some care homes would collect the participant data. Now only care homes that will allow their staff to collect data will be included in the trial. It is proposed that the care home staff will receive training via the app video link to enable them to use the devices safely and achieve good data quality.

The video will not be used for or with participants, only for staff assistance and training.

Each time it is used, the opening screen of the app will assess whether the participant is displaying the symptoms of COVID-19 infection.

It does this by requiring the staff member to follow an on-screen protocol as follows:

- At the start of each shift the staff member shall record their own temperature and answer COVID symptoms questions. If COVID is suspected, the app will prevent further use by that staff member until a negative result from a formal COVID-19 test is entered or until seven days have passed from the last symptoms. If the staff member is not suspected of having COVID0-19 the app continues as before.
- 2. Take the participant's temperature using the provided digital thermometer in forehead temperature mode to avoid physical contact with the participant.
- 3. Answer the guestion does the participant have a new, continuous cough.
- 4. Answer the question has the participant reported a loss or change to their sense of smell or taste.
- 5. Answer the question does the participant have diarrhoea or vomiting.

If the measured temperature is 38.0°C (was 38.2°C but GP advice has caused us to change the threshold temperature to 38.0°C or greater or (previously AND) the answer is yes to any of the questions 1 - 3, the app will indicate to the staff member through a screen message that the participant may have COVID-19. In this case, the participant shall be temporarily excluded from the trial and will have no further involvement until they have been formally tested for COVID-19.

If the test returns negative, the participant shall continue to be included in the trial.

If the participant's test returns positive and the participant is well enough in the view of their doctor and the member of staff to allow re-inclusion in the trial, the trial shall continue with a completely separate set of devices reserved for use on participants with confirmed infection. The original devices and monitoring equipment that first recorded the suspected infection for a participant will not work for that participant unless a negative test result is entered or until seven days after confirmed infection and the symptoms have passed. The digital thermometer that was used to measure the participant's temperature is easily cleanable and will be made safe by the care home's enhanced hygiene procedures. The participant shall be considered clear of risk of passing infection seven days after being tested positive for COVID-19 and the symptoms have passed and monitoring shall continue with the original set of devices.

If the participant's test returns unclear, void, borderline or inconclusive, the participant shall be temporarily excluded from the trial until a further test with a positive or negative outcome is available.

If the participant has a negative result but has diarrhoea or vomiting, the participant shall be temporarily excluded from the trial until 48 hours after the symptoms have stopped.

The app records a full time and date stamped audit log of all actions.

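### Appendix E's COVID-19 alert rule cites questions 1 to 3, but the participant symptom questions are printed as items 3 to 5

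*Protocol*

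**What the plan says.** Appendix E (Protocol section 27) describes one on-screen sequence that care home staff follow in the app.

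- The first entry concerns the staff member: "At the start of each shift the staff member shall record their own temperature and answer COVID symptoms questions". It has its own consequence: the app locks out a staff member with suspected infection until a negative test is entered or seven days have passed since the last symptoms.
- Item 2 is a measurement: "Take the participant's temperature using the provided digital thermometer in forehead" mode.
- Item 3 asks whether the participant has a new, continuous cough.
- Item 4 reads: "Answer the question has the participant reported a loss or change to their sense of smell or taste".
- Item 5 reads: "Answer the question does the participant have diarrhoea or vomiting".

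The alert rule follows the list. It has a temperature limb at 38.0°C, joined to a symptom limb by "or greater or (previously AND) the answer is yes". The symptom limb reads: "the answer is yes to any of the questions 1 - 3, the app will indicate to the staff member" that the participant may be infected. The participant is then temporarily excluded and "will have no further involvement until they have been formally tested for COVID-19".

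A later rule deals with gastrointestinal symptoms after testing: "If the participant has a negative result but has diarrhoea or vomiting, the participant shall be temporarily excluded from the trial". This further exclusion ends once 48 symptom-free hours have passed.

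**The concern.** The range in the alert rule does not match the list it refers to. Two of its three numbers point to entries that are not participant symptom questions, and two of the three participant symptom questions lie outside it.

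This matters because the two limbs of the rule are now alternatives. For a resident below 38.0°C, the cited range alone decides whether the alert, the temporary exclusion and the formal test follow. The same trigger starts device segregation: the equipment that first recorded a suspected infection stops working for that participant until Appendix E's conditions are met. Section 5.4 lists cross infection through reused devices as a risk, and Appendix E describes the cohort as especially vulnerable to COVID-19. Appendix F adds that care home staff have no medical qualification, so they depend on the app's message being right.

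**Working it through.** There is no figure to reproduce. The check sets the cited range beside the printed list. The first entry's own number is missing from the text read from the PDF, but it comes directly before item 2. Numbers 2 to 5 are printed, so the mismatch is in the document itself.

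| Printed item | Content | Participant symptom question? | In range 1 to 3? |
|---|---|---|---|
| 1 (by position) | Staff member's own temperature and symptom check | No | Yes |
| 2 | Participant's temperature | No, and already covered by the temperature limb | Yes |
| 3 | Cough | Yes | Yes |
| 4 | Smell or taste | Yes | No |
| 5 | Diarrhoea or vomiting | Yes | No |

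**Overlap.** The cited set is {1, 2, 3} and the participant symptom questions are {3, 4, 5}. They share {3}, so 1 of 3 symptom questions is inside the range and 2 of 3 are outside.

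**What the phrase could mean.**

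1. Printed numbers: among the symptom questions, only cough triggers the alert.
2. First to third participant question: items 3, 4 and 5 all trigger it. Exactly three entries are worded as questions about the participant, so this reading fits well.
3. Numbering left over from a list without the staff entry: the old items 1 to 3 would have been temperature, cough, and smell or taste. Diarrhoea or vomiting would then not be a trigger. This is conjecture; the document does not show such a list.

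**What the printed numbers miss under each possible intention.**

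- Intended {3, 4, 5}: {4, 5} are missed, 2 of 3.
- Intended {3, 4}: {4} is missed, 1 of 2.

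Item 4, smell or taste, is missed in both cases.

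**Does the 48-hour rule settle item 5?** No. It applies to a participant with a negative result who has diarrhoea or vomiting. That participant may have been tested because of item 5, or because of a temperature, cough or smell/taste answer with item 5 present as well.

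**Is the range superseded text?** No. The sentence notes a former threshold of 38.2°C and a former AND, but the range 1 to 3 belongs to the current wording.

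**The case against.** The strongest reply is that nobody could sensibly apply the printed numbers. The rule speaks of questions answered yes. Item 2 is a measurement, cannot be answered yes, and is already the other limb of the sentence. The first entry does contain symptom questions, but they are put to the staff member and cannot show that the participant is infected. Taken as the first to third participant questions, the rule is complete. Under that reading, and under the leftover-numbering reading, smell or taste is included. The count of 2 out of 3 missed therefore belongs only to a literal reading that the sentence hardly supports. Staff also do not apply the sentence by hand, because the app raises the alert. Section 10.10 adds a check of general health at each visit.

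Much of this stands. A numbering slip is the most likely explanation, the counts hold only for the printed numbers, and no harm is shown because the app logic and the SOP are not available. Three things remain. The sentence is wrong as written, and nothing elsewhere in the Protocol corrects it. The two sensible readings disagree on item 5, so calling it a slip does not settle the rule. The general health check has no stated link to alert, exclusion or testing, so it does not replace the trigger.

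**Conclusion.** The concern holds as a minor participant-safety correction. By the printed numbers the alert rule covers 1 of 3 participant symptom questions. It leaves out smell or taste under either plausible intention, and diarrhoea or vomiting as well if that is meant as a trigger.

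That the numbers do not match is certain. What was intended for item 5 is not. A resident would be missed only if the app or the SOP was built on the printed numbers, and the document does not show that it was. It gives no symptom frequencies, so no number of affected residents can be stated. Outcomes, sample size and analysis are not affected.

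**What to change.** Replace the numeric reference in Appendix E with named triggers: participant temperature of 38.0°C or greater, new continuous cough, and loss or change of smell or taste. Add diarrhoea or vomiting if the sponsor confirms that it is meant to trigger the alert on its own. If all three questions are intended, changing the range to 3 to 5 is enough, though named triggers would survive any later renumbering.

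Then check that the app configuration and the care home staff SOP match the corrected sentence.

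The cost is one phrase in Appendix E, one confirmation from the sponsor and one check of the app and the SOP. No visits or participants are added.

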## 28. Appendix F Informing the Care Home Staff to take Action Based on Device Readings

Readings from medical devices recording vital signs can be used together with a clinical knowledge of a patient's conditions to provide an informed view of whether a patient is suffering an exacerbation that should be investigated. An individual reading from a vital signs monitoring device may cause unnecessary worry and not indicate a serious condition for a particular patient. Care home staff are not medically qualified and will not in general be able to interpret occasional out of bounds readings.

However, values from some devices that give a reliable indication irrespective of the patient's specific condition may be used to aid common sense judgment that action should be taken. The medical device monitoring phone is programmed to show vital signs according to the NEWS2 scoring system used in hospitals to give an 'at a glance' display of a patient's overall status. The SpO2 alerts and colour scheme used is that of Scale 1 in the NEWS2 scoring system. SpO2 on its own is not considered to be a safe warning sign as medical knowledge of the patient's condition is needed to decide on a suitable alert threshold.

In Reassure, values that will cause a red alert to be triggered to help the care home worker decide if a patient's condition might require attention are as follows:

<= 40 or >= 131 bpm (at rest)

Respiration <= 8 or >= 25 BPM

Temperature >= 38.0°C (COVID-19 threshold)

Systolic Blood Pressure <= 90 or >220 mmHg

Pulse

ECDS_UniqueID	Sort1	Sort2	ECDS_Group	ECDS_Description	SNOMED_Code	SNOMED_Description	Notes
						Hypertensive disorder, systemic	
2018111100	11	11	Circulation / blood	Hypertension	38341003	arterial (disorder)	-
2018111500	11	15	Circulation / blood	History of anticoagulant therapy	161647008	History of anticoagulant therapy (situation)	_
2018112100	11	21	Circulation / blood	Ischaemic heart disease	414545008	Ischemic heart disease (disorder)	_
2018113100	11	31	Circulation / blood	Cardiac pacemaker in situ	441509002	Cardiac pacemaker in situ (finding)	_
2018114300	11	43	Circulation / blood	Congestive heart failure	42343007	Congestive heart failure (disorder)	_
2018114500	11	45	Circulation / blood	Left heart failure	85232009	Left heart failure (disorder)	-
2018114900	11	49	Circulation / blood	Heart failure	84114007	Heart failure (disorder)	-
2018115100	11	51	Circulation / blood	Mitral valve disorder	11851006	Mitral valve disorder (disorder)	_
2018118100	11	81	Circulation / blood	Congenital cardiac failure	206586007	Congenital cardiac failure (disorder)	_
2018211100	21	11	Respiratory	Asthma	195967001	Asthma (disorder)	-
2018212100	21	21	Respiratory	Chronic obstructive lung disease	13645005	Chronic obstructive lung disease ( disorder )	_
2018212300	21	23	Respiratory	Chronic bronchitis	63480004	Chronic bronchitis (disorder)	_
2018214100	21	41	Respiratory	Pulmonary emphysema	87433001	Pulmonary emphysema (disorder)	_
2018215100	21	51	Respiratory	Respiratory failure	409622000	Respiratory failure (disorder)	_
2018311100	31	11	Gastrointestinal	Dysphagia	40739000	Dysphagia (disorder)	_
2018312100	31	21	Gastrointestinal	Jaundice	18165001	Jaundice (finding)	-
2018312500	31	25	Gastrointestinal	Liver function tests abnormal	166603001	Liver function tests abnormal (finding)	_
2018511100	51	11	Endocrine / Rheumatology	Diabetes mellitus	73211009	Diabetes mellitus (disorder)	_
2018515100	51	51	Endocrine / Rheumatology	Rheumatoid arthritis	69896004	Rheumatoid arthritis (disorder)	_
2018551100	55	11	Renal / urology	Retention of urine	267064002	Retention of urine (disorder)	_
2018552100	55	21	Renal / urology	Renal impairment	236423003	Renal impairment (disorder)	_
2018553100	55	31	Renal / urology	Chronic kidney disease	709044004	Chronic kidney disease (disorder)	_

		Ī		Chronic interstitial		Chronic interstitial nephritis	
2018555100	55	51	Renal / urology	nephritis	60926001	(disorder)	_
2018555500	55	55	Renal / urology	Small kidney	236448000	Small kidney (disorder)	_
2018556100	55	61	Renal / urology	Multiple renal cysts	253883006	Multiple renal cysts (disorder)	_
				Congenital cystic kidney		Congenital cystic kidney disease	
2018556300	55	63	Renal / urology	disease	82525005	(disorder)	_
2018556900	55	69	Renal / urology	Polycycstic kidney disease	765330003	Autosomal dominant polycystic kidney disease (disorder)	New term Oct 2018
2018611100	61	11	Neurology	Epilepsy	84757009	Epilepsy (disorder)	_
2018612100	61	21	Neurology	Multiple sclerosis	24700007	Multiple sclerosis (disorder)	_
2018613100	61	31	Neurology	Cerebral infarction	432504007	Cerebral infarction (disorder)	_
2018613300	61	33	Neurology	Cerebrovascular accident	230690007	Cerebrovascular accident (disorder)	
2018613700	61	37	Neurology	Cerebrovascular disease	62914000	Cerebrovascular disease (disorder)	-
2018615100	61	51	Neurology	Subarachnoid haemorrhage	21454007	Subarachnoid intracranial hemorrhage (disorder)	_
2018615500	61	55	Neurology	Cerebral haemorrhage	274100004	Cerebral hemorrhage (disorder)	_
2018618100	61	81	Neurology	Aphasia	87486003	Aphasia (finding)	
2018618500	61	85	Neurology	Hemiplegia	50582007	Hemiplegia (disorder)	ECDS uniqueID modified April 2018
2018711100	71	11	Psychiatry / psychology	Anxiety disorder	197480006	Anxiety disorder (disorder)	_
2018712100	71	21	Psychiatry / psychology	Depressive disorder	35489007	Depressive disorder (disorder)	_
2018712500	71	25	Psychiatry / psychology	History of deliberate self harm	314550003	History of deliberate self harm (situation)	_
2018712900	71	29	Psychiatry / psychology	Bipolar disorder	13746004	Bipolar disorder (disorder)	_
2018716500	71	65	Psychiatry / psychology	Eating disorder	72366004	Eating disorder (disorder)	_
2018716700	71	67	Psychiatry / psychology	Schizotypal personality disorder	31027006	Schizotypal personality disorder (disorder)	_
2018717100	71	71	Psychiatry / psychology	Schizophrenia	58214004	Schizophrenia (disorder)	
2018717500	71	75	Psychiatry / psychology	Psychotic disorder	69322001	Psychotic disorder (disorder)	_
2018717700	71	77	Psychiatry / psychology	Delusional disorder	48500005	Delusional disorder (disorder)	_

•	i .	i .	I	1	•	•	1
2018751100	75	11	Developmental	Developmental delay	248290002	Developmental delay (disorder)	_
2018752100	75	21	Developmental	Autistic disorder	408856003	Autistic disorder (disorder)	-
2018753100	75	31	Developmental	Learning difficulties	161129001	Learning difficulties (finding)	_
				Developmental academic		Developmental academic disorder	
2018754100	75	41	Developmental	disorder	1855002	(disorder)	_
2018811100	81	11	Sensory / age related	Dementia	52448006	Dementia (disorder)	_
2018811500	81	15	Sensory / age related	Alzheimer's disease	26929004	Alzheimer's disease (disorder)	_
2018812100	81	21	Sensory / age related	Elderly fall	298344006	Elderly fall (finding)	_
2018814100	81	41	Sensory / age related	Blindness - both eyes	193699007	Blindness - both eyes (disorder)	_
2018814500	81	45	Sensory / age related	Blindness of one eye	22950006	Blindness of one eye (disorder)	_
2018814900	81	49	Sensory / age related	Registered blind	170727003	Registered blind (finding)	_
2018815100	81	51	Sensory / age related	Complete deafness	8531006	Complete deafness (disorder)	_
2018815200	81	52	Sensory / age related	Bilateral deafness	162344009	Bilateral deafness (disorder)	_
2018815300	81	53	Sensory / age related	Profound acquired hearing loss	737050003	Profound acquired hearing loss (disorder)	SNOMED definition and or code amended April 2018
2018815400	81	54	Sensory / age related	Profound sensorineural hearing loss	700454004	Profound sensorineural hearing loss (disorder)	_
2018815500	81	55	Sensory / age related	Severe hearing loss	3561000119106	Severe hearing loss (disorder)	_
2018911100	91	11	Social / drug / alcohol	Smoker	77176002	Smoker (finding)	_
2018912100	91	21	Social / drug / alcohol	Lives alone	105529008	Lives alone (finding)	_
2018915100	91	51	Social / drug / alcohol	Alcohol abuse	15167005	Alcohol abuse (disorder)	_
2018916100	91	61	Social / drug / alcohol	Recreational drug use	26416006	Drug abuse (disorder)	_
2018916200	91	62	Social / drug / alcohol	Misuses drugs	361055000	Misuses drugs (finding)	_
_	_	_	_	_	28728008	_	Code Deprecated 31.03.2019
					525791000000105		Code Deprecated 31.03.2019

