# 10. DESCRIPTION OF STUDY INTERVENTION(S), COMPARATORS AND STUDY PROCEDURES (CLINICAL)

This project is observational only. It is not interventional.

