### 19.4. Other Ethical Considerations

No children will be included in this study. This study is non-interventional and data will not be analysed until the interim report and final report stages.

In the unlikely event that one of the study professional HCAs observes a severe worsening of condition in a participant that is not known to the participant's medical team and such 10that the abnormality was medically important, they will discuss the implications with the participant's care team. Participants will not be informed. It is important to note that remote monitoring data are not collected for diagnostic purposes, and therefore the monitoring is not a substitute for a clinical appointment. Rather, the monitoring is intended for research purposes only.

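### Red alerts to care-home staff use the same vital signs that are meant to predict unscheduled care, while the protocol calls the study non-interventional; in care homes the estimated association is open to bias of unknown direction

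*Protocol*

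**What the plan says.** Section 10 states: "This project is observational only. It is not interventional". Section 19.4 says that the data are not collected for diagnosis and that "the monitoring is intended for research purposes only". Section 12.3 repeats that the study is non-interventional and defers all analysis until it is complete.

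Appendix F (section 28) carries the title "Informing the Care Home Staff to take Action Based on Device Readings". It has the phone display vital signs in NEWS2 colours and lists "values that will cause a red alert to be triggered to help the care home worker decide" whether a resident may need attention. The listed values cover pulse, respiration, temperature and systolic blood pressure. Appendix F says that readings of this kind "may be used to aid common sense judgment that action should be taken".

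The same signs appear in the device lists by condition group in section 7, and section 5.2 applies every device to every Phase 1 participant. The primary outcome in section 6 relates device-based prediction of exacerbation to actual attendances in GP records. Section 9.4 blinds only the data analysts. Under Appendix E, only care homes whose own staff take the readings will take part.

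**The concern.** A study of prediction needs the outcome to arise independently of the prediction. Here the person who takes the reading also sees the alert and can act on it before the outcome is recorded.

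Two effects follow, with opposite signs:

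- **Prompted contact.** An alert leads staff to seek urgent care that would not otherwise have been sought. A false positive is then counted as a true positive, and the association looks stronger.
- **Averted event.** An alert leads to early attention and the attendance does not happen. A true positive is then counted as a false positive, and the association looks weaker.

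Phase 1 takes place wholly in care homes. Its results decide which devices Phase 2 participants receive (sections 5.2 and 7) and feed the interim report that precedes Phase 2 (section 12.2). A distortion there would carry forward.

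**Working it through.** **Does alert overlap with predictor and outcome?** Alert inputs: pulse, respiration, temperature, systolic pressure (Appendix F). Predictors: heart rate, respiration rate, temperature and blood pressure are in the section 7 lists, with weight, peak flow, blood sugar, ECG, SpO2 and CO2. Outcome: unscheduled care in GP records (sections 5.2 and 6). The loop is in the text.

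**Who is exposed?** Appendix F addresses care-home staff only, and no alert is described for people who self-monitor at home. All of Phase 1 is exposed. In Phase 2, section 5.2 lets Phase 1 participants (up to 100) continue and recruits the rest through GP surgeries, to take part from their own homes. That gives at most 100/500 = 20%. The Stage II table in section 12.1 appears to place 400 of 500 in nursing or care homes (80%), but its layout did not survive extraction, so this is uncertain.

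**The plan's own figures.** With sensitivity 0.85, half-width 0.05 and incidence 0.35, N(SN) = 1.96² × 0.85 × 0.15 / 0.05² / 0.35 = 559.8, matching the stated 560. The Stage II table's first month gives 0.35 × 500 = 175 patients with an episode and 325 without.

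**Illustration.** Inputs: 175 events, 325 non-events. Specificity 0.80 (section 12.1) gives 65 false positives and 260 true negatives. Assumptions: every model-positive triggers a red alert; half of false positives lead to an urgent contact, or 20% of true positives are averted; incidence and accuracy are equal in both settings. Let s be the share of the sample exposed to alerts.

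*Prompted*, x = 0.5 × 65 × s, true sensitivity assumed 0.70 (122.5 true positives):

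- s = 1: x = 32.5; sensitivity (122.5 + 32.5)/(175 + 32.5) = 0.747; specificity 260/(325 − 32.5) = 0.889.
- s = 0.2: x = 6.5; 129/181.5 = 0.711; 260/318.5 = 0.816.
- s = 0.8: x = 26; 148.5/201 = 0.739; 260/299 = 0.870.

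*Averted*, y = 0.2 × 148.75 × s, true sensitivity 0.85 (section 12.1):

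- s = 1: y = 29.75; sensitivity (148.75 − 29.75)/(175 − 29.75) = 0.819; specificity 260/(325 + 29.75) = 0.733.
- s = 0.2: y = 5.95; 142.8/169.05 = 0.845; 260/330.95 = 0.786.
- s = 0.8: y = 23.8; 124.95/151.2 = 0.826; 260/348.8 = 0.745.

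The two cases start from different sensitivities. From 0.85, the fully exposed prompted case gives (148.75 + 32.5)/207.5 = 0.873, a rise of 2.3 points, with specificity again 0.889.

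**Relaxing the overlap.** Suppose only half of model-positives trigger a red alert and 30% of those alerts change the outcome, with incidence 0.35 and accuracy 0.85/0.80 in a fully care-home sample. As proportions of the sample, true positives are 0.2975, false positives 0.13 and true negatives 0.52.

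- Averted: 0.5 × 0.3 × 0.2975 = 0.0446; sensitivity 0.2529/0.3054 = 0.828; specificity 0.52/0.6946 = 0.749.
- Prompted: 0.5 × 0.3 × 0.13 = 0.0195; sensitivity 0.317/0.3695 = 0.858; specificity 0.52/0.6305 = 0.825.

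**The case against.** Five points deserve weight.

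1. *Reach.* A reader might infer that the whole study is distorted by 5 to 9 points. The documents do not support that: alerts are described for care-home staff only, and on section 5.2's account at most a fifth of Phase 2 is exposed. The resulting shift of 0.5 to 1.6 points lies well inside the planned 5-point half-width. This stands.
2. *Alert is not prediction.* Red alerts fire at fixed values of four signs. The model uses each participant's own norms (section 10.7) and other devices, so a model-positive need not be an alert. This stands, and the overlap is a separate unknown.
3. *Safety escalation in an observational study.* Appendix F offers alerts as an aid to judgement, so not every alert leads to action. Section 19.4 already has research staff raise severe worsening with the care team. This softens the contradiction but does not remove it: section 19.4 describes an unlikely event, Appendix F a routine display at each reading.
4. *A matter for the analysis plan.* With-and-without analyses commonly belong there, and a plan not shown may contain them. It could not reconcile the protocol's statements, however, or recover an alert-to-action link that was never recorded. Appendix E says "The app records a full time and date stamped audit log of all actions", but within the COVID-19 procedures; it does not say that a clinician contact made outside the app is captured.
5. *Limits of the remedy.* Removing prompted contacts also removes some that would have happened anyway, and it does not restore averted ones. Care-home and home participants differ in setting, in who measures and in devices. Both limits stand and shape the fix.

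**Conclusion.** The point holds for care-home participants: all of Phase 1 and the residents who continue into Phase 2. There the protocol describes monitoring that can change its own outcome while declaring itself non-interventional, and the estimated association or accuracy mixes prediction with the effect of alerts.

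The direction is unknown, because prompted contacts raise apparent accuracy and averted events lower it. A reader might infer that accuracy will be inflated, or will be understated; the documents support neither, since they give no rate of alerts, actions or conversions. The size is likewise not computable. With half of model-positives alerting and 30% of those averted, the fall in specificity in a fully exposed cohort (0.800 to 0.749) is about the planned half-width of 0.05. At 20% exposure, under the conversion shares used above, the shift is at most about 2 points. All of this rests on assumed shares, assumed overlap, and equal incidence and accuracy in both settings.

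This should be corrected, but it does not invalidate the design.

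**What to change.** - **Reconcile the text.** Bring Appendix F into line with every statement that the study has no intervention or that monitoring is for research only: the synopsis and sections 6, 7, 9.4, 10, 11, 12.3 and 19.4. No view is taken here on the alerts, their thresholds or their use.
- **Record the link.** In the app, record each red alert, its time and any clinician contact that followed. State how a contact in the GP record is attributed to an alert.
- **Analyse it.** In care-home participants, report the primary correlation of section 6 (and sensitivity and specificity, if used) with and without alert-prompted contacts. Add a sensitivity analysis over an assumed range for averted events.
- **Show the settings apart.** Present care-home and home results separately, labelled descriptive.

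The cost is slight extra recording by staff who already use the app, some judgement in linking contacts to alerts, and one further sensitivity analysis.
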